### 5.3 Analysis Populations

Agreement and authorization of patients included/excluded from each analysis population will be conducted prior to database lock of the study. A data review meeting will be conducted prior to database lock and confirm the patients in each analysis set population. Impact of Covid-19 pandemic on the missed data, missed visits or dropouts will be assessed during this meeting and appropriate decisions on population counts will be taken.

### 5.3.1 Full Analysis Set (FAS)

The Full Analysis Set (FAS) includes all study participants who sign informed consent.

### 5.3.2 Safety Population (SAF)

The Safety Population (SAF) is defined as all study participants in the Full Analysis Set who meet all screening criteria, are enrolled, and receive at least one dose of the assigned treatment during the runin period. This population will be used for safety analyses.

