5.1 Procedures and Study Visits

Patients will attend a total of four visits during the study for a duration of 12 weeks. A total number of 290 patients will be screened considering 25% of drop-out rate, to obtain at least 216 patients complete the run-in period and start with the assessment period. The description of the activities, procedures, and tests to be performed at each visit is detailed below:

Screening Visit 1 (Week -4)

The following procedures/assessments will be performed during the Screening Visit 1:

- Informed consent
- Interactive Web Response System (IWRS) registration to register the treatment allocation
- Verification of inclusion and exclusion criteria
- Collection and review of Medical history
- Collection and review of Prior and concomitant medications
- Collection of Demographic data
- Recording of concurrent diseases and medical conditions

MENARINI	Corporate Medical Department		
Identification Number	Version Number	State	Effective date
FORM-000050125	2.0, CURRENT	Effective	08, Jan 2021

- Physical Examination
- Vital sign measurements
- BP Measurement
- ECG
- Perform Urine Pregnancy Test (UPT) to female of child-bearing potential
- Perform Local Laboratory Tests
- Adverse Event (AE) and Serious Adverse Event (SAE) Assessment
- Paper instruction to use automatic blood pressure device, including patient's diary provided to the patient
- Automatic blood pressure device provided to patients: to be used in case of Covid-19 pandemic situation emergency procedures (Section 2.3)

Patients meeting all inclusion criteria and none of the exclusion criteria will enter the run-in period on the same day and will receive monotherapy of ZOF 30 mg or AML 5 mg.

- Patients who are already on therapy with ZOF 30 mg or AML 5 mg will be provided with the same medication
- Patients taking any other CCBs (refer to section Subject Study Phases
 Duration for allowed CCBs) will be provided with AML 5 mg, and patients
 taking any other ACE-i will be provided with ZOF 30 mg. Patients entering
 this phase in therapy with ZOF 30 mg or AML 5 mg should be as close as
 possible to a 1:1 ratio.

Visit 2 (Week 0 ± 2 days):

The following procedures/assessments will be performed at Visit 2:

- Recording of concurrent diseases and medical conditions
- Concomitant medications
- Vital sign measurements
- Physical Examination
- BP Measurement
- Urine pregnancy test (UPT)

MENARINI	Corporate Medical Department		

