reviewing and filing these results. Note: Patients who will be reported with an abnormal renal function (creatinine clearance <30 mL/min) and/or abnormal liver enzyme parameters (alanine aminotransferase [ALT] or aspartate aminotransferase [AST] level of >2.5 × upper limit of normal [ULN] or bilirubin level >1.5 × ULN) will be withdrawn from treatment and study.

The following parameters Haematology and Serum Chemistry parameters will be assessed:

Haematology	Serum Chemistry
Red blood cell	ALT
White blood cell	Albumin
Haemoglobin	Alkaline phosphatase
Haematocrit	AST
Platelets	Direct bilirubin
Neutrophils	Total bilirubin
Lymphocytes	Total protein
Monocytes	Creatinine
Eosinophils	Blood urea nitrogen
Basophils	Creatine kinase
Neutrophils absolute	GGT
Lymphocytes absolute	Triglycerides
Monocytes absolute	Cholesterol
Eosinophils absolute	High- and low-density lipoprotein
Basophils absolute	Chloride
	eGFR
	Blood glucose
	Potassium
	Uric acid

AE/SAE Assessments

The assessment of adverse events (AEs) by seriousness and relationship will be performed at all visits. AEs that occur after a patient has signed the ICF and prior to exposure to study drug will be recorded on the case report form and will not be considered treatment emergent adverse events (TEAEs).

MENARINI	Corporate Medical Department		
Identification Number	Version Number	State	Effective date
FORM-000050125	2.0, CURRENT	Effective	08, Jan 2021

Management of clinical trial during Pandemic COVID-19

Since December 2019, an outbreak of respiratory disease caused by a novel coronavirus, first detected in Wuhan City, Hubei Province, China, has been detected in nearly all countries of the world. The virus has been named "SARS-CoV-2" and the disease it causes has been named "Coronavirus Disease 2019" (COVID-19). On 08 March 2020, the World Health Organization (WHO) declared the COVID-19 outbreak a global pandemic.

The COVID-19 public health emergency may impact the conduct of clinical trials of medical products. In response to the pandemic, various health authorities have issued guidelines to maintain the integrity of ongoing clinical studies

Summary of Changes in Study-Related Procedures as a Result of the COVID-19 Pandemic

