12.3 Analysis Populations

A total of three populations will be used for all summaries and analyses. Study participants who have satisfied the population criteria will be classified in the designated population and will only be included in analyses for which they have available data.

Data analysis will be performed using the following analysis sets.

The Safety Population

The Safety population is defined as all study participants who sign the informed consent, meet all screening criteria, are enrolled, and receive at least one dose of the assigned treatment during the run-in period. This population will be used for safety analyses.

The Efficacy Population

The Efficacy population is defined as all study participants in the Safety population who complete the 4-week run-in period and the Visit 2 blood pressure assessment. This will be population for efficacy analysis.

The Per-Protocol Population

The Per-Protocol (PP) population is defined as all study participants in the Efficacy population who were dosed according to protocol, complete the required study visits, and do not experience any major protocol deviations that may impact the primary efficacy assessment through end of treatment.

HEVARIN	Corporate Medical Department		
Identification Number	Version Number	State	Effective date
FORM-000050125	2.0, CURRENT	Effective	08, Jan 2021

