### 8 Safety Analyses (Endpoint 2.5)

**Endpoint 2.5**: Safety and tolerability of the monotherapies (ZOF 30 mg and AML 5 mg) after 4 weeks of therapy and of the extemporaneous combination (ZOF 30 mg and AML 5 mg or AML 10 mg) after eight weeks of treatment.

The variables for endpoint 2.5 are laboratory tests, physical examination, vital signs, 12-lead ECG, and incidence of AEs/SAEs, each of which are discussed in the subsections below.

Safety analyses will be performed on the SAF population. Results will be presented as described in section 5.5 unless otherwise specified.

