### 8.2 Adverse Events, Adverse Drug Reactions, and Deaths

Adverse Events (AEs) are any untoward medical occurrence in a clinical trial patient administered a medicinal product and which does not necessarily have a causal relationship with this treatment.

*Treatment Emergent AEs (TEAEs)* are defined as AEs that occur only once treatment has started (after the first dose of monotherapy of ZOF or AML). Thus, all AEs that occur in both the monotherapy and combined therapy periods will be considered treatment-emergent.

Adverse Drug Reactions (ADRs) are defined as AEs that have a relationship of "certain," "probable," "possible," or "unassessable."

All AEs will be coded using the Medical Dictionary for Regulatory Activities (MedDRA) version 24.1 or later.

The following tabulations will be produced for the monotherapy period and the combination therapy periods for the SAF population:

- Monotherapy Period (Day of Visit 1 through day before Day of Visit 2)
  - All treatment-emergent AEs (TEAEs)

- Severe TEAEs
- Adverse Drug Reactions (ADRs)
- TEAEs leading to study discontinuation
- Serious TEAEs (TESAEs)
- o Serious ADRs
- TESAEs with outcome of death
- Combination Therapy Period (Day of Visit 2 through Day of Visit 4)
  - All treatment-emergent AEs (TEAEs)
  - Severe TEAEs
  - Adverse Drug Reactions (ADRs)
  - TEAEs leading to study discontinuation
  - Serious TEAEs (TESAEs)
  - Serious ADRs
  - TESAEs with outcome of death

Key guidelines for counting incidence proportions of AEs/TEAEs/ADRs (collectively referred to as AEs for the remainder of this section) are as follows:

- When a patient has the same AE reported multiple times during an analysis period based on MedDRA terminology (SOC or PT), the patient will only be counted once within a level of MedDRA in an AE incidence table.
- When assessing investigator reported relationship to study drug of the AEs, if an AE reported multiple times changes in causal relationship during an analysis period for a patient, the event with highest relatedness will be presented. Related AEs (i.e., ADRs) will include those reported as "certain," "probable," "possible," or "unassessable" by the investigator.

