#### Table 14.1.2 Analysis Populations and Exclusions (Full Analysis Set)

		All Patients
Analysis Populations [7]	Statistic	(N=xx)
Included in Safety (SAF) [1,4]	n (%)	xx (xx.x)
Excluded from Safety (SAF)	n (%)	xx (xx.x)
Did Not Meet all Screening Criteria	n (%)	xx (xx.x)
Did Not Receive At Least One Dose During Run-In	n (%)	xx (xx.x)
Included in Efficacy (EFF) [2,5]	n (%)	xx (xx.x)
Excluded from Efficacy (EFF)	n (%)	xx (xx.x)
Did Not Complete Run-In Period	n (%)	xx (xx.x)
Did Not Meet Continuation Criteria at Visit 2	n (%)	xx (xx.x)
Did Not Complete Visit 3 or 4	n (%)	xx (xx.x)
Included in Per Protocol (PP) [3,6]	n (%)	xx (xx.x)
Excluded from Per Protocol (PP)	n (%)	xx (xx.x)
Not Dosed According to Protocol	n (%)	xx (xx.x)
Did Not Complete Required Study Visits	n (%)	xx (xx.x)
Major Protocol Deviation That May Impact the Primary Efficacy Assessment	n (%)	xx (xx.x)

[1] Percentage based on number of All Patients.

[2] Percentage based on number of subjects included in SAF.

[3] Percentage based on number of subjects included in EFF.

[4] Safety Population (SAF): All study participants who sign informed consent, meet all screening criteria, are enrolled, and receive at least one dose of the assigned treatment during the run-in period.

[5] Efficacy Population (EFF): All study participants in the Safety Population who complete the 4-week run-in period and meet continuation criteria at Visit 2 [uncontrolled BP (sitting SBP/DBP > 130/80 mmHg), tolerate treatment, and fall within 80-120% treatment adherence] and have at least one available post baseline primary efficacy assessment (from Visit 3 or 4).

[6] Per Protocol Population (PP): All study participants in the Efficacy Population who were dosed according to the protocol (80% - 120% adherence reported for each dosing visit), complete the required study visits (Visits 1, 2, 3, 4), and do not experience any major protocol deviations that may impact the primary efficacy assessment through end of treatment.

[7] If subjects are excluded for more than one reason, they will only be counted for the first listed reason.

Source: Listing 16.2.3

Program Name: XXXX.SAS

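### As worded, the Safety Population requires eligibility as well as dosing, so a dosed patient later found ineligible could be left out of every safety table and the adverse event and death listings

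*SAP*

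**What the plan says.** SAP 5.3.2 takes the Full Analysis Set (everyone who consents) and keeps those "who meet all screening criteria, are enrolled, and receive at least one dose of the assigned treatment" during the run-in. Protocol 12.3 has the same rule: "all study participants who sign the informed consent, meet all screening criteria, are enrolled, and receive at least one dose of the assigned treatment". The condition is therefore common to both documents and is not a slip in the SAP.

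The set then governs all safety reporting. SAP section 8 states: "Safety analyses will be performed on the SAF population". SAP 8.2 adds: "The following tabulations will be produced for the monotherapy period and the combination therapy periods for the SAF population". In the table and listing index, every table under 1.1.3 Safety is assigned to this population, and so are the adverse event, adverse event detail and death listings (16.2.7.1 to 16.2.7.3). Shell Table 14.1.2 gives "Did Not Meet all Screening Criteria" as a reason for exclusion from the Safety Population, on a separate row from not having been dosed.

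**The concern.** A safety set is normally defined by exposure. Here it is defined by exposure and eligibility together. If an entry violation comes to light after the first dose, the literal rule removes an exposed patient from both numerator and denominator of every safety table, and that patient's events from the adverse event listings.

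Safety and tolerability of the monotherapies and of the combinations is a secondary endpoint (SAP Endpoint 2.5). One serious event in one such patient would be enough to make the reported safety record incomplete. The Efficacy Population is drawn from the Safety Population and the Per Protocol Population from the Efficacy Population, so the same patient also leaves the primary analysis. An eligibility violation would then act on the main efficacy set and not only on the Per Protocol set.

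**Working it through.** The plan gives no figure on this point to reproduce. The check is a reading of the passages against each other, followed by an illustration under stated assumptions.

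**1. Is the case foreseen?** Yes. Protocol section 10 lists, among the reasons for withdrawal, an exclusion criterion that was not recognised at entry. Shell Table 14.1.1 has a discontinuation row for meeting an exclusion criterion. It is separate from screen failures and is expressed as a percentage of those enrolled. Screening and entry are close together: "Patients meeting all inclusion criteria and none of the exclusion criteria will enter the run-in period on the same day" (Protocol 5.1).

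**2. Apply the definitions to such a patient.**

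| Condition | Met? |
|---|---|
| Signed consent | yes |
| Enrolled | yes |
| At least one run-in dose | yes |
| All screening criteria met | no |

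Result: in the Full Analysis Set, but not in the Safety Population. Hence not in the Efficacy Population (SAP 5.3.3 starts from the Safety Population), and not in the Per Protocol Population (SAP 5.3.4 starts from the Efficacy Population).

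**3. Is there a rule that puts the patient back?** None was found. The data review meeting in SAP 5.3 confirms who is in each set before database lock, but has no criterion for keeping dosed patients. SAP 6.2 grades deviations for the purpose of the Per Protocol Population only.

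**4. Where would the patient still be seen?** In Full Analysis Set outputs: disposition with the reason for discontinuation (SAP 6.1), protocol deviations (SAP 6.2), the list of exclusions from populations (Listing 16.2.3) and, if Visit 2 data exist, the Visit 2 monotherapy summaries run on that set. None of these tabulates or lists adverse events.

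**5. Could a reader count such patients?** Not from Table 14.1.2. A patient with several reasons is counted under the first listed one, and the eligibility row precedes the no-dose row. Ordinary undosed screening failures and dosed ineligible patients would share one row.

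**6. Illustration of size (assumptions, not trial figures).** Let N patients be dosed, a share r be found ineligible after dosing, and an event have incidence p, taken to be the same in these patients as in the rest. Then m = r × N patients leave the Safety Population, m × p patients with the event are expected to be lost, and the chance of losing at least one is 1 − (1 − p)^m. With N = 290:

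| r | m | Safety Population | p | m × p | Chance of losing at least one |
|---|---|---|---|---|---|
| 1% | 3 | 290 − 3 = 287 | 10% | 0.3 | 1 − 0.90^3 = 27% |
| 10% | 29 | 290 − 29 = 261 | 10% | 2.9 | 1 − 0.90^29 = 95% |
| 1% | 3 | 287 | 1% | 0.03 | 1 − 0.99^3 = 3% |
| 10% | 29 | 261 | 1% | 0.29 | 1 − 0.99^29 = 25% |

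The base of 290 is itself uncertain. The Protocol synopsis and sections 5, 5.1 and 6 give it as the number screened; Protocol 12.2 and SAP 4.6 give it as the number enrolled. A smaller dosed number gives smaller values.

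**The case against.** The best answer is that the clause means no more than that the patient was not a screening failure. Protocol 6.2.3 defines a screening failure as a consented patient who does not enter the run-in, and Protocol section 8 places the check of all entry criteria at the Screening Visit. On that reading, anyone who entered the run-in and took drug has passed screening, whatever is discovered later. Listing 16.2.3 supports it by joining failure of the screening criteria with not enrolling in a single reason. Since Table 14.1.2 starts from everyone who consented, it needs a row for undosed screening failures in any case. SAP 8.1.4.2 also shows an inclusive intention, treating unreturned drug as taken so that patients stay in the safety analyses.

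Much of this stands. The reading is available, and the Table 14.1.2 row does not by itself prove that dosed patients are to be removed. But the reading is never stated. If it is what was intended, the clause adds nothing to the requirement of being enrolled and can be deleted without loss. SAP 8.1.4.2 concerns tablet counts and does not alter the population definition.

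A reader might also infer that the Visit 1 laboratory samples will regularly produce such patients. The documents do not support that. The renal and liver cut-offs in Protocol 8.2, after which patients "will be withdrawn from treatment and study", are withdrawal rules. Exclusion criteria 6 and 8 contain no laboratory cut-offs and rest on the investigator's judgement or on clinical relevance. No passage says whether Visit 1 results arrive before or after the first dose.

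**Conclusion.** The point holds as a defect of definition. On the literal text, an exposed patient with an entry violation found later is outside the Safety Population, and nothing in either document keeps that patient in. At best the text is ambiguous, and a programmer following it literally would exclude the patient.

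The size is unknown. The documents give no rate of late-found violations, and the illustration only shows how the loss would scale with an assumed one.

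Two stronger conclusions should not be drawn. The first is that the omission favours the drugs: nothing shows that violators would mainly have renal, hepatic or cardiac disease, and violations of age, blood pressure range or prior dose are equally possible. The second is that these patients vanish from the report: they remain in the disposition and deviation outputs, and the recording and expedited reporting of events under Protocol 9.9 and 9.10 do not depend on this population.

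**What to change.** - In Protocol 12.3, SAP 5.3.2, the footnote to Table 14.1.2 and the footnote to Listing 16.2.3, define the Safety Population as all participants who received at least one dose of study treatment, regardless of any eligibility violation found later.
- In Table 14.1.2, restrict the screening-criteria row to patients who failed screening and were not dosed.
- Report eligibility violations as protocol deviations and assess them for the Per Protocol Population. With the Efficacy Population still nested in the Safety Population, a dosed patient who satisfies the other conditions of SAP 5.3.3 then stays in it.

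The cost is minor rewording in both documents and the shells. Safety counts may look slightly less favourable.

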### 5.3.3 Efficacy Population (EFF)

The Efficacy Population (EFF) is defined as all study participants in the Safety Population who complete the 4-week run-in period and meet continuation criteria at Visit 2 [uncontrolled BP (sitting SBP/DBP > 130/80 mmHg), tolerate treatment, and fall within 80-120% treatment adherence] and have at least one available post baseline primary efficacy assessment (from Visit 3 or 4). This population will be used for efficacy analyses.

### 5.3.4 Per Protocol Population (PP)

The Per Protocol Population (PP) is defined as all study participants in the Efficacy Population who were dosed according to the protocol (80% - 120% adherence reported for each dosing visit), complete the required study visits (Visits 1, 2, 3, 4), and do not experience any major protocol deviations that may impact the primary efficacy assessment through end of treatment.

Whether to include or exclude the patients from PP set will be finalized in the data review meeting prior to database lock.

### 5.4 Covariates and Subgroups

Exploratory endpoints 3.1, 3.2, and 3.4 will be analyzed on the following subgroups:

- Patients who were on ZOF 30 mg or AML 5 mg at Visit 1 (Week -4) and continued the same therapies.
- Patients who switched to ZOF 30 mg or AML 5 mg from any other ACE-i or CCBs at Visit 1 (Week -4).

Exploratory endpoint 3.4 will also be analyzed on the following subgroups, such that each subgroup above will be further stratified by the subgroups below:

- Hypertension grade (Grade 1 or 2) reported at Visit 1
  - Reported in the eCRF at Visit 1
- Presence of diabetes and/or hypercholesterolemia at Visit 1
  - Reported as ongoing Medical History event at Visit 1 using MedDRA terms below

Protocol Term	MedDRA Preferred Term	
Diabetes	Diabetes mellitus	
Hypercholesterolemia	Hypercholesterolemia	

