### 6.4 Medical History

Medical History will be coded using the Medical Dictionary for Regulatory Activities (MedDRA) version 24.1 or later. Medical history will be presented in a by-patient data listing for the SAF population and will include the System Organ Class (SOC) and Preferred Term (PT) for each medical condition.

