### 7.4.2 Proportion of Patients (Endpoints 3.3 and 3.4)

**Endpoint 3.3**: Monotherapy: number and proportion of patients achieving the BP goal (sitting BP  $\leq 130/80$  mmHg) at Visit 2 (Week 0). Combination therapy: number and proportion of patients achieving the BP goal (sitting BP  $\leq 130/80$  mmHg) at Visit 3 (Week 4).

**Endpoint 3.4**: Monotherapy: number and proportion of patients divided in subgroup by the hypertension grade, the presence of diabetes and/or of hypercholesterolemia achieving the BP goal (sitting BP  $\leq$ 130/80 mmHg) at Visit 2 (Week 0). Combination therapy: number and proportion of patients divided in subgroup by the hypertension grade, the presence of diabetes and/or of hypercholesterolemia achieving the BP goal (sitting BP  $\leq$ 130/80 mmHg) at Visit 3 (Week 4) and Visit 4 (Week 8).

Endpoints 3.3 and 3.4 will be analyzed using a logistic MMRM to assess the proportion of patients achieving the BP goal (sitting BP  $\leq$ 130/80 mmHg). The models will be built as follows:

- Endpoint 3.3
  - *Response* = achieving BP goal (sitting BP ≤130/80 mmHg)
  - *Covariates* = treatment subgroup, study visit, treatment subgroup-by-visit interaction, baseline BP values
  - *Random effect* = patient
  - Covariance matrix = unstructured
    - In the event of lack of model convergence, other covariance structures may be used.
    - If all logistic MMRM fail to converge, this endpoint will be analyzed as described in section 7.4.2.1 below.

- Endpoint 3.4 by hypertension grade
  - *Response* = achieving BP goal (sitting BP ≤130/80 mmHg)
  - *Covariates* = treatment subgroup, study visit, treatment subgroup-by-visit interaction, baseline BP values
  - *Random effect* = patient
  - Covariance matrix = unstructured
    - In the event of lack of model convergence, other covariance structures may be used.
    - If all logistic MMRM fail to converge, this endpoint will be analyzed as described in section 7.4.2.1 below.
  - Stratification factor = Baseline hypertension grade
- Endpoint 3.4 by presence of diabetes and/or of hypercholesterolemia
  - *Response* = achieving BP goal (sitting BP ≤130/80 mmHg)
  - *Covariates* = treatment subgroup, study visit, treatment subgroup-by-visit interaction, baseline BP values
  - *Random effect* = patient
  - *Covariance matrix* = unstructured
    - In the event of lack of model convergence, other covariance structures may be used.

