# Statistical Analysis Plan

BMI (kg/m2)	n	xx	xx	хх
	Mean (SD)	xx.x (xx.xx)	xx.x (xx.xx)	xx.x (xx.xx)
	Median	xx.x	xx.x	xx.x
	Min, Max	xx, xx	xx, xx	xx, xx
Smoking Status				
Never Tobacco Smoker	n (%)	xx (xx.x)	xx (xx.x)	xx (xx.x)
Former Tobacco Smoker	n (%)	xx (xx.x)	xx (xx.x)	xx (xx.x)
Daily	n (%)	xx (xx.x)	xx (xx.x)	xx (xx.x)
Occasional	n (%)	xx (xx.x)	xx (xx.x)	xx (xx.x)
Current Tobacco Smoker	n (%)	xx (xx.x)	xx (xx.x)	xx (xx.x)
Daily	n (%)	xx (xx.x)	xx (xx.x)	xx (xx.x)
Occasional	n (%)	xx (xx.x)	xx (xx.x)	xx (xx.x)
Undisclosed	n (%)	xx (xx.x)	xx (xx.x)	xx (xx.x)
e-Cigarettes	n (%)	xx (xx.x)	xx (xx.x)	xx (xx.x)
Medical History	n (%)	xx (xx.x)	xx (xx.x)	xx (xx.x)
Hypertension Grade 1	n (%)	xx (xx.x)	xx (xx.x)	xx (xx.x)
Hypertension Grade 2	n (%)	xx (xx.x)	xx (xx.x)	xx (xx.x)
Diabetes mellitus	n (%)	xx (xx.x)	xx (xx.x)	xx (xx.x)
Hypercholesterolemia				
Treatment at Run-In	n (%)	xx (xx.x)	xx (xx.x)	xx (xx.x)
Zofenopril 30 mg	n (%)	xx (xx.x)	xx (xx.x)	xx (xx.x)
Amlodipine 5 mg	n (%)	xx (xx.x)	xx (xx.x)	xx (xx.x)
Other ACE-i	n (%)	xx (xx.x)	xx (xx.x)	xx (xx.x)
Other CCB				
Study Site	n (%)	xx (xx.x)	xx (xx.x)	xx (xx.x)
201	n (%)	xx (xx.x)	xx (xx.x)	xx (xx.x)
202	n (%)	xx (xx.x)	xx (xx.x)	xx (xx.x)
(repeat for all sites)		· · ·		

Source: Listings 16.2.4.1, 16.2.4.2 Program Name: XXXX.SAS

Date: DDMMMYYYY

Programming Note:

Patients will be classified as either ZOF/AML 30/5 mg or ZOF/AML 30/10 mg such that no patients are counted in both groups. That is, even though patients in the ZOF/AML 30/10 mg group are also exposed to the ZOF/AML 30/5 mg treatment, they will only be included in the ZOF/AML 30/10 mg and All Patients columns, not within the ZOF/AML 30/5 mg column. Patients that do not belong to the ZOF/AML 30/5 mg or ZOF/AML 30/10 mg group will be included only in the All Patients column.

• In the medical history section, the first two rows (hypertension grade) will come from raw EDC data RUNDIS.RHYPEGRD and the second two rows (diabetes and hypercholesterolemia) will come from raw EDC data MH as per usual.

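### The comorbidity strata of exploratory Endpoint 3.4 rest on one MedDRA Preferred Term per condition, so a patient with diabetes or hypercholesterolemia coded only to other terms is tabulated as Absent

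*SAP*

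**What the plan says.** SAP 5.4 (Covariates and Subgroups) makes "Presence of diabetes and/or hypercholesterolemia at Visit 1" one of the stratifying variables for Endpoint 3.4. The condition must be "Reported as ongoing Medical History event at Visit 1 using MedDRA terms below". The table under that rule has a column headed "MedDRA Preferred Term" and two rows: diabetes is mapped to "Diabetes mellitus", and hypercholesterolemia is mapped to the Preferred Term of the same name.

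SAP 6.4 has medical history coded in MedDRA 24.1 or later, and the listing "will include the System Organ Class (SOC) and Preferred Term (PT) for each medical condition". SAP 7.4.2 then specifies a logistic model headed "Endpoint 3.4 by presence of diabetes and/or of hypercholesterolemia", with this flag as the stratification factor. The shell for Table 14.2.4.4.2 has two comorbidity columns, Present and Absent, each divided into patients who continued their earlier drug and patients who switched.

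For the baseline table (14.1.3), the programming note says that "the second two rows (diabetes and hypercholesterolemia) will come from raw EDC data MH as per usual". It does not cite the SAP 5.4 term table.

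The protocol synopsis and Protocol Section 4 define the subgroup clinically, by presence of diabetes and/or hypercholesterolemia, with no coding term attached.

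**The concern.** The SAP turns a clinical concept into one dictionary code per condition and names nothing wider: no higher-level term, no standard grouping, no list of related terms, no medical review of coded history. SAP Section 10, which records departures from the protocol, does not mention the narrowing.

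Coding assigns each history entry its own Preferred Term. If a site's entry for a type of diabetes, or for a cholesterol disorder, is coded to some other term, the rule does not recognise it. A programmer who follows SAP 5.4 as written would then report a patient with a documented condition under a column that says the condition is absent. At stake are the content of the two columns of Table 14.2.4.4.2 and the number of patients left in the Present column to support its odds ratios.

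**Working it through.** The documents give no figure to reproduce on this point, so the check is mainly of text.

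1. **Rule.** SAP 5.4 gives one Preferred Term per condition. Neither the rest of the SAP nor the protocol widens it.
2. **Source.** Hypertension grade has its own eCRF field (Table 14.1.3 programming note). Diabetes and hypercholesterolemia do not; they come only from coded medical history.
3. **Allocation.** The stratum is a composite of the two conditions. A patient is Present if either listed term is ongoing at Visit 1. With only two columns, a patient with neither listed term is Absent, whatever else the history contains.
4. **Contrast tested.** SAP 7.4 defines the groups compared as continued versus switched patients. SAP 7.4.2 and the table shell place that odds ratio inside each comorbidity column. No planned test compares Present with Absent.

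To show scale, let N be the number of patients, P the true share with either condition, and s the share of those patients who carry at least one listed term. Defined this way, s already allows for patients missed on one condition but caught by the other.

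- Misplaced patients = N × P × (1 − s)
- Size of the Absent column = N × (1 − P × s)
- Share of Absent that is misplaced = P × (1 − s) / (1 − P × s)

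N = 216 is the planned number starting the assessment period (SAP 4.6 and 4.1). It is used only as a round scale: the Efficacy Population also requires a post-baseline value, and the Visit 2 part of the table uses the Full Analysis Set. P and s are assumptions.

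| P | s | With either condition | Left in Present | Misplaced | Absent column | Share misplaced |
|---|---|---|---|---|---|---|
| 20% | 80% | 43.2 | 34.6 | 8.6 | 181.4 | 4.8% |
| 20% | 50% | 43.2 | 21.6 | 21.6 | 194.4 | 11.1% |
| 40% | 80% | 86.4 | 69.1 | 17.3 | 146.9 | 11.8% |
| 40% | 50% | 86.4 | 43.2 | 43.2 | 172.8 | 25.0% |

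For example, 216 × 0.40 × (1 − 0.50) = 43.2 misplaced, out of 216 × (1 − 0.40 × 0.50) = 172.8 in Absent. At s = 100% nobody is misplaced, whatever P is.

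**The case against.** The strongest reply is that the harm depends on something the documents do not show: whether these patients' histories are coded to other Preferred Terms. That is right, and it is why the size can only be illustrated. It does not remove the defect, which is that the SAP makes no provision for any other term. The question can be settled from the study's own coded history, since Listing 16.2.13 prints every Preferred Term. The same listing makes any miscoding visible and recoverable.

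It is also fair to say that the reach is small: one of two stratifications of the last exploratory endpoint. That stands, and it sets the severity.

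A reader might go further in four ways that the documents do not support.

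- *That the misplacement biases results toward zero.* That would describe a Present-versus-Absent comparison, with coding unrelated to response. The planned odds ratios are within-column, continued versus switched, and mixing affected patients into Absent has no predictable direction there.
- *That every patient coded to another term is lost.* The and/or composite keeps anyone whose other condition carries its listed term.
- *That Table 14.1.3 certainly understates comorbidity.* Its note names the medical history data, not the SAP 5.4 rule. It is affected only if the same terms are used.
- *That a spelling difference would make the lipid term match nobody.* This needs both the dictionary's spelling and literal text matching. The documents show neither.

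**Conclusion.** The concern holds in a limited form, as a minor point. SAP 5.4 defines the comorbidity stratum more narrowly than the protocol concept. Any patient with either condition but neither listed term is labelled Absent in Table 14.2.4.4.2. The consequence is mislabelled strata and a smaller Present column.

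The number affected is unknown. Under the assumed ranges (20% to 40% with either condition, 50% to 80% of those carrying a listed term, 216 patients) it is about 9 to 43, and it is zero if all histories are coded to the two listed terms. Only exploratory Endpoint 3.4 is affected, and possibly the matching rows of Table 14.1.3. The primary and secondary analyses do not use this flag.

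**What to change.** Replace the two-row table in SAP 5.4 with a definition at the level of the condition: all Preferred Terms that denote diabetes mellitus of any type, and all Preferred Terms that denote "hypercholesterolemia", with borderline lipid terms decided by medical review.

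Draw the list from the coded terms alone, without reference to blood pressure outcomes. This matters because the study is open-label. Freeze the list before database lock. The data review meeting in SAP 5.3 is a convenient occasion, but its stated task is to confirm analysis populations and assess the impact of Covid-19, so this would need adding to its agenda. Use the same two flags in Tables 14.1.3 and 14.2.4.4.2.

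The cost is a short term list and one medical judgement on borderline lipid terms. No new data or visits are needed. If every affected patient already carries a listed term, nothing in the output changes.
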